14.3.2 Exploratory endpoints

This pilot study will use exploratory, descriptive, and observational methods to

- 1) Evaluate the attitude of patients and physicians toward randomization and explore reasons for treatment preference
- 2) Evaluate whether the ability to assess fitness for intensive chemotherapy can be improved by an augmented treatment-related mortality (TRM) score that includes additional (co-

morbidity) factors, and to compare the ability of physicians of the prediction algorithm(s) and physician to assess the likelihood of early death

3) Estimate differences between patients treated with lower-intensity G-CLAM and those treated with higher-intensity G-CLAM with regard to anti-leukemic efficacy (response, duration of response) and survival, QOL, and medical resource utilization as well as care cost

Importantly, this trial is not powered to detect statistically significant differences between the study arms for these clinically important endpoints. Rather, the primary goal is to estimate outcomes with both treatment intensities to inform a subsequent larger study, should follow-up investigation appear warranted.

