14.1 Treatment allocation

Treatment will be allocated based on patient preference. If agreeable to randomization, participants will be allocated to either lower-intensity G-CLAM or higher-intensity G-CLAM in a 1:1 ratio using a computer-generated random list of numbers. Randomization will occur in blocks of 4. Participants not agreeable to randomization will be allocated to lower-intensity G-CLAM or higher-intensity G-CLAM as per subject's preference.

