14.2 Sample Size and Power

This study will enroll up to 50 subjects.

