14.3 Primary/Exploratory Endpoints/Hypotheses and Analytical Methods

14.3.1 Primary endpoint

The primary objective of this study is to evaluate the feasibility of randomizing patients to either intensive or non-intensive induction and post remission chemotherapy. We will consider randomization feasible (i.e. a subsequent, larger study would be designed as a randomized trial) if the true proportion of patients willing to be randomized is 60% or higher. With 50 patients in a feasibility study and accounting for the sample variation associated with 50 patients, we will consider randomization feasible if at least 52% of the patients agree to be randomized (i.e. 26 or more of 50 patients agree to be randomized). If the true proportion willing to be randomized is 60%, the probability of observing 52% or more willing to be randomized is 90%. The probability of having 26 or more of the 50 patients agree to be randomized is only 6% if the true randomization agreement rate is 40%, and <1% if the true randomization agreement rate is 30% or lower, providing good operating characteristics not only to avoid a false negative result but also a false positive result. If one treatment arm closes prematurely (see section on monitoring below), we will conclude that randomization is not feasible, and the remaining patients will be treated on the remaining arm. Continuation of enrollment into that remaining arm will allow us to gain additional experience and provide more precise estimates of treatment efficacy and treatment-related toxicities.

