19.0 APPENDICES

APPENDIX A: TREATMENT-RELATED MORTALITY (TRM) SCORE

Calculation of Simplified Treatment-Related Mortality (TRM) Score

Includes covariates: performance status (PS), age, platelet count, albumin, secondary AML, white blood cell count (WBC), peripheral blood blast percentage, and creatinine

Score = $100/(1+e^{(-x)})$, with $x = -4.08 + 0.89*PS + 0.03*age - 0.008*platelet count - 0.48*albumin + 0.47*(have secondary AML) + 0.007*WBC - 0.007*(peripheral blood blast percentage) + 0.34*creatinine$

Probability of TRM Above and Below Various Simplified TRM Score Cut-offs

TRM Score Interval	Patients below/within/above TRM Score Interval (%)	TRM Probability if below TRM Score Interval (%)	TRM Probability if within TRM Score Interval (%)	TRM Probability if above TRM Score Interval (%)
0 – 1.9	0/20/80	-	1	12
1.91 – 3.9	20/20/60	1	2	16
3.91 – 6.9	40/20/40	1	7	20
6.91 – 9.2	60/10/30	3	7	24
9.21 – 13.1	70/10/20	4	12	31
13.11 – 22.8	80/10/10	5	20	41
22.81 – 100	90/10/0	6	41	-

From: Walter RB, Othus M, Borthakur G, Ravandi F, Cortes JE, Pierce SA, Appelbaum FR, Kantarjian HM, Estey EH. Prediction of early death after induction therapy for newly diagnosed acute myeloid leukemia with pretreatment risk scores: a novel paradigm for treatment assignment. *J Clin Oncol.* 2011;29(33):4417-4424.

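### The exploratory arm comparison pools randomized patients with those who chose their arm and specifies no adjustment for the TRM score known at entry

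*Combined protocol and SAP*

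**What the plan says.** Item 3 of section 14.3.2 aims to "Estimate differences between patients treated with lower-intensity G-CLAM and those treated with higher-intensity G-CLAM" in response, duration of response, survival, QOL, resource use and cost. The method is given only in the lead-in: "This pilot study will use exploratory, descriptive, and observational methods to". No estimator, covariate or analysis set is named. Exploratory objective 2.2.3 likewise groups patients by the intensity they received.

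Section 14.1 allocates consenting patients "in a 1:1 ratio using a computer-generated random list of numbers", in blocks of 4 with no stratification factor. Patients who decline randomization take the arm they prefer. Section 14.2 states "This study will enroll up to 50 subjects", and section 14.3.1 calls randomization feasible if "26 or more of 50 patients agree to be randomized".

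Criterion 3.1.3 requires a TRM score of at least 13.1, so the score exists for every eligible patient. The Appendix A table, "Probability of TRM Above and Below Various Simplified TRM Score Cut-offs", gives early death of 20% within 13.11–22.8 and 41% within 22.81–100. Each band holds 10% of the source cohort. Item 2 of section 14.3.2 uses the score for prediction; nothing uses it in the arm comparison.

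**The concern.** At the 60% willingness the plan hopes for, 20 of 50 patients choose their own arm; at the 52% threshold, 24 do. The documents themselves suggest that such choices follow fitness. The physician survey (Appendix E) offers, as a reason, that the patient is too unfit for the higher intensity. Section 1.0 infers from an earlier randomized trial that physicians can tell fit from less fit patients. It also warns that selection bias may explain the apparent advantage of intensive therapy, and gives that as the reason to randomize.

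If frailer patients lean towards the lower dose, a comparison by treatment received makes the higher dose look safer than it is, and the reverse holds if the lean is the other way. Section 14.3.2 says the purpose is to estimate outcomes at both intensities to inform a larger study. A bias of this kind would pass into that study's planning assumptions, and the interval around the estimate would not show it.

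**Working it through.** **The plan's own figures.** Exact binomial: P(26 or more of 50) = 0.902 at a true rate of 60%, 0.057 at 40% and 0.0009 at 30%. These match the stated 90%, 6% and <1%. The plan gives no precision for the arm differences.

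**Inputs from the documents.** Early death 20% (lower band) and 41% (upper band), a gap of 21 points and a ratio of 41/20 = 2.05; 50 patients; 60% or 52% randomized.

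**Assumptions.** Half of patients fall in each band, because each holds 10% of the Appendix A cohort. Final arms are 25 v 25. Randomized patients are balanced on score. Within a band, early death is the same on both regimens.

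**Effect of self-selection.** The average rate is (20 + 41)/2 = 30.5%. Let c be the number of choosers per arm and s the share of them that follow the score (lower-band patients to one arm, upper-band to the other). Then

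false difference = (c/25) × (2s − 1) × 21 points.

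| Randomized | c | s = 0.75 | s = 1 (upper bound) |
|---|---|---|---|
| 60% (30 of 50) | 10 | 4.2 | 8.4 |
| 52% (26 of 50) | 12 | 5.0 | 10.1 |

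Arm rates under complete sorting:
- 60% randomized: (15 × 30.5 + 10 × 20)/25 = 26.3% v (15 × 30.5 + 10 × 41)/25 = 34.7%.
- 52% randomized: (13 × 30.5 + 12 × 20)/25 = 25.5% v (13 × 30.5 + 12 × 41)/25 = 35.5%.

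**Effect of chance imbalance in randomized patients.** At 15 v 15 with 15 upper-band patients in all, the hypergeometric probability that the arms differ by 3 or more such patients is 0.466, and by 5 or more 0.143. The shifts are 3/15 × 21 = 4.2 points and 5/15 × 21 = 7.0 points. The sampling SE of the difference is √(2 × 0.305 × 0.695/15) = 16.8 points, so these are 0.25 and 0.42 of one SE.

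The two bands explain 0.25 × 0.21²/(0.305 × 0.695) = 5% of the variance in early death, so adjustment gains little precision. In simulation with no treatment effect, the SD of the difference, unadjusted and then with a two-stratum Mantel-Haenszel risk difference, is:
- 13 v 13: 18.1 and 18.0 points
- 15 v 15: 16.8 and 16.7 points
- 25 v 25: 13.0 and 12.8 points

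**The case against.** Five arguments can be made for leaving the text alone.

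1. *The plan does not prescribe raw differences.* This is correct. A reader might infer that item 3 commits to an unadjusted contrast, but the text is silent. The accurate statement is that no adjustment is specified.

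2. *Randomized arms need no adjustment.* Largely correct. A reader might infer from the doubling of early death in Appendix A that a few patients of chance imbalance distort the randomized comparison. The working shows otherwise: the shifts are under half an SE, and adjustment removes only 0.1–0.2 points of an SD of 13–18. The sponsor's adjusted comparison of G-CLAM with 7+3 (section 1.0) used an external, non-randomized control. It is a precedent for the choosers, not for randomized arms.

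3. *Section 14.4 already compares regimens among randomized patients.* It does, but for monitoring. Nothing carries that restriction into item 3.

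4. *The pilot disclaims power.* The plan says "this trial is not powered to detect statistically significant differences between the study arms for these clinically important endpoints". That answers a complaint about testing, not one about avoidable bias in an estimate meant for planning.

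5. *Restricting the main contrast loses information.* This is a real cost. Dropping from 25 to 15 per arm raises the SE from 13.0 to 16.8 points. Even under complete sorting at 60% randomized, the pooled estimate's root mean squared error is √(13.0² + 8.4²) = 15.5 points. But that sum counts bias through the TRM score alone, and the pooled interval would not reveal the bias. Reporting both groups keeps the data.

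**Conclusion.** The point stands as one about self-selection. Item 3 pools two groups whose arms were assigned by different mechanisms and does not say that the entry TRM score will be used. On the assumptions above, the false early-death difference is about 4 to 8 points at 60% randomized and up to 10 points at 52%; the upper figures need every chooser to sort by score.

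The size is illustrative. The band rates come from an older cohort given intensive therapy, section 1.0 says early deaths have since fallen, and whether the gradient holds at the lower dose is unknown. The half-and-half band split, the equal arms and the degree of sorting are assumptions. Early death is not listed in item 3 and reaches it only through survival. A reader might carry the same shift over to response, QOL or cost, but the documents give no gradient by score for those outcomes, so no shift can be computed. The primary feasibility endpoint is unaffected.

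**What to change.** Add one paragraph to section 14.3.2, item 3:

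- The main between-arm estimate uses randomized patients, analysed as randomized.
- Patients who chose their arm are reported separately, with a TRM-adjusted estimate beside the unadjusted one. Use the continuous score as a single covariate, or, for binary outcomes, two strata (13.1–22.8 and above 22.8).
- The TRM score is tabulated by arm and by mode of allocation, so that readers can see whether choice followed it.

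The cost is slightly more analysis work and a smaller sample for the main contrast: about 30 patients at 60% randomized, or 26 at the threshold. No new data or extra patients are needed, because the score is already an eligibility requirement. Adjustment for the score will not remove confounding by other factors, so the choosers' estimate should still be labelled observational.

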14.4 Monitoring for efficacy and early mortality

This study will evaluate each regimen separately, and also compare regimens among patients who are randomized. Details for both sets of analyses are provided below.

Within-arm monitoring for efficacy and early mortality

We will enroll patients in 2 stages in order to allow for early stopping for unacceptable differences in early mortality or inefficacy. Early mortality will be defined as death for any reason on or before day 28 after starting therapy. Inefficacy will be evaluated using MRD^{neg} CR.

We will use our ongoing clinical trial using a CPX-351 in medically less fit adults with AML or high-grade MDS will provide “historical” control data for both inefficacy and early mortality. In this trial (FHCRC #2642.00), which used essentially identically inclusion/exclusion criteria, we have so far treated 37 subjects at a CPX-351 dose of 32 units/m². Among these, 8 patients achieved an MRD^{neg} CR (22%). Ten patients (27%) died within 28 days of treatment initiation; at least 4 of these subjects experienced early disease progression as main cause of death, highlighting the balance between treatment efficacy and potential toxicity.

In the first stage, 10 patients will be accrued to each arm, either in a randomized or non-randomized fashion. Each arm will be evaluated separately for early death and inefficacy stopping rules. Accrual may temporarily be held while outcome data on these patients matures.. As some patients may choose to not be randomized, the 2 treatment arms may be evaluated at a different time point for early stopping.

1) Lower-dose Arm: After 10 patients have been accrued to the lower-dose arm, we will evaluate for early death and inefficacy.

Early death: If the number of early deaths is 5 or higher, accrual will stop with the conclusion that the arm is too toxic for further randomization. If the true early mortality rate is 30% or less, the probability of observing 5 or more early mortality events is 15%.

Inefficacy: If there are 0 patients with MRD^{neg} CR, accrual will stop with the conclusion that the arm is not efficacious enough for further randomization. If the true MRD^{neg} CR rate is 22%, the probability of observing 0 MRD^{neg} CRs in 10 patients is 8%.

2) Higher-dose Arm: After 10 patients have been accrued to the higher dose arm, we will evaluate for early death and inefficacy.

Early death: If the number of early deaths is 5 or higher, accrual will stop with the conclusion that the arm is too toxic for further randomization. If the true early mortality rate is 30% or less, the probability of observing 5 or more early mortality events is 15%.

Inefficacy: If there are 0 patients with MRD^{neg} CR, accrual will stop with the conclusion that the arm is not efficacious enough for further randomization. If the true MRD^{neg} CR rate is 22%, the probability of observing 0 MRD^{neg} CRs in 10 patients is 8%.

Between-arm monitoring for efficacy and early mortality

After enrollment of at least 10 patients in each arm (at which point one arm may have more than 10 patients accrued due to slower accrual in one arm), we will compare the two arms for relative mortality and efficacy. If, based on Fisher's exact test, the early mortality rate is significantly higher in one arm at the alpha =10% level (this criterion will be met if, for example, both arms have accrued 10 patients one arm has 0 early mortality events and the other arm has 4), accrual will stop in that arm with the conclusion that the arm with the higher early mortality rate is too toxic for further randomization. In addition, if based on Fisher's exact test, the MRD^{neg} CR rate is significantly higher in one arm compared to the other at the alpha = 10% level (for example, this criterion will be met if both arms have accrued 10 patients and one arm has 2 MRD^{neg} CRs and the other has 7), the accrual will stop in that arm with the conclusion that the arm with the lower MRD^{neg} CR rate is not efficacious enough for further randomization.

If accrual does not stop in both arms, up to a total of 50 patients will be accrued.

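### The early-death rule is applied only after 10 patients are accrued to an arm, so an arm whose closure is already certain at its fifth early death may keep accruing; a minor point with a one-sentence remedy

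*Combined protocol and SAP*

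**What the plan says.** All of this is in section 14.4 of the combined protocol and SAP.

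- First stage: "In the first stage, 10 patients will be accrued to each arm, either in a randomized or non-randomized fashion".
- Definition: "Early mortality will be defined as death for any reason on or before day 28 after starting therapy".
- Timing, lower-dose arm: "After 10 patients have been accrued to the lower-dose arm, we will evaluate for early death and inefficacy".
- Timing, higher-dose arm: "After 10 patients have been accrued to the higher dose arm, we will evaluate for early death and inefficacy".
- Boundary, the same in both arms: "If the number of early deaths is 5 or higher, accrual will stop".
- Stated operating characteristic: 15% probability of 5 or more early deaths in 10 if the true rate is 30% or less.
- Inefficacy, at the same look: accrual stops with 0 MRD-negative CRs in 10, stated as 8% likely if the true rate is 22%.
- Historical control: "Ten patients (27%) died within 28 days of treatment initiation", out of 37.

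Accrual may be held while first-stage outcomes mature, but this is optional. The between-arm comparison also waits for at least 10 patients in each arm. Outside section 14.4, section 9.0 provides for independent committee review of toxicities at scheduled meetings, section 12.0 for committee review at least annually and as needed, and section 17.0 reserves a right of the investigator and IRB to terminate at any time. None of these names the fifth early death, or any other count, as a trigger before the tenth patient.

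**The concern.** The count of early deaths in an arm can only rise. If five of the first seven patients have died by day 28, the count at 10 must be at least 5, and the protocol's own conclusion that the arm is too toxic for further randomization is already fixed. Under the written rule, patients eight to ten may still be randomized to that arm or choose it, although their outcomes cannot change the decision.

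The situation is not far-fetched. Eligibility requires a TRM score of at least 13.1 (section 3.1.3), and Appendix A gives a 31% TRM probability above the interval ending at 13.1. The higher-dose regimen was tested in medically fit adults, with a median TRM score of 2.85 in the maximum-dose cohort (section 1.0), so early mortality in the present population is not known from those data. Detecting a high rate is what this rule is for.

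**Working it through.** **Inputs.** From section 14.4: n = 10 per arm, boundary r = 5, early death = death by day 28, reference rate 30%, historical rate 10/37 = 27%. The 50% and 60% rates are illustrative. The documents give neither an accrual rate nor the timing of deaths within the 28 days, so both are assumed below.

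**Step 1: reproduce the stated figures.** Exact binomial, P(X ≥ 5 | n = 10, p = 0.30) = 0.1503, matching the stated 15%. It is exact at 30% and an upper bound below that. The inefficacy figure is 0.78^10 = 0.0834, matching 8%.

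**Step 2: the rule with stopping at the fifth death.** Let K be the position, in order of enrolment, of the fifth patient to die early. Then P(K = k) = C(k−1, 4) p^5 (1−p)^(k−5), and the arm closes if K ≤ 10. The event K ≤ 10 is the same as 5 or more deaths in 10, so the closing probability must agree:

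| True early-death rate | Look at 10 | Stop at fifth death |
|---|---|---|
| 27% | 0.1037 | 0.1037 |
| 30% | 0.1503 | 0.1503 |
| 50% | 0.6230 | 0.6230 |
| 60% | 0.8338 | 0.8338 |

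The feasibility figures in section 14.3.1 (90%, 6%, <1%) concern willingness to be randomized and do not depend on this timing. An arm curtailed for deaths would have closed anyway, so the chance of closing an arm under either within-arm rule is also unchanged.

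**Step 3: upper limit on the benefit.** If outcomes were known at once, the fifth death would fall at patient 9 or earlier with probability 0.066, 0.099, 0.50 and 0.73 at 27%, 30%, 50% and 60%. Among arms that close at a 50% rate this is 0.500/0.623 = 80%. The mean number enrolled after the fifth death, per closing arm, is 1.26, 1.32, 1.98 and 2.47 respectively, with a maximum of 5.

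**Step 4: benefit with the 28-day lag.** Deaths take time to occur, so fewer patients are spared. Simulation assuming one patient per arm every 7 or every 21 days and death times uniform over days 1-28 (ranges run from 7-day to 21-day accrual):

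| True rate | Arms where the change acts before patient 10 | Mean spared per closing arm | Mean spared per arm opened |
|---|---|---|---|
| 27% | 3-6% | 0.5-1.1 | 0.05-0.11 |
| 30% | 4-9% | 0.5-1.2 | 0.07-0.17 |
| 50% | 29-46% | 0.9-1.8 | 0.6-1.1 |
| 60% | 49-70% | 1.2-2.2 | 1.0-1.9 |

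The last column is the third multiplied by the closing probability from step 2, before rounding. Faster accrual gives the smaller figures.

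**The case against.** The case against runs on four lines.

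**Discretion already exists.** A reader might infer that the protocol obliges the site to fill the arm to 10 regardless. It does not: sections 9.0, 12.0 and 17.0 allow review and termination, and at a single center the investigator would know of five deaths. This stands as mitigation. None of these routes carries a number, so none replaces a trigger.

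**The benefit is small at the documents' own rates.** This stands. At 27-30% the saving is at most about 0.17 patients per arm opened. A reader who saw only the 50% and 60% figures might infer a large exposure problem, which the documents do not support.

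**The change is not entirely free.** This also stands. A curtailed arm yields fewer patients for the outcome estimates that section 14.3.2 calls the primary goal of the exploratory analyses. Its naive early-death rate, five divided by the number enrolled, is affected by the stopping. It would also never reach the 10 per arm required for the between-arm comparison, which could in principle bear on the other arm: 5/10 against 1/15 MRD-negative CRs gives Fisher p = 0.023, below the 10% level, although one CR passes the within-arm rule. Such cases should be uncommon, and the plan does not say whether a closed arm is still compared.

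**A broader rewrite would do harm.** One might be tempted to tie the whole within-arm look to completion of day 28. That would also govern inefficacy, while section 6.5 allows the response marrow up to day 35 and a second induction course. An arm could then be judged on immature response data, and the stated 8% would no longer describe the rule. The change must therefore be confined to early death.

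**Conclusion.** The point holds as a minor improvement. As written, the early-death rule acts only at 10 accrued, so an arm whose closure is already certain may keep accruing. Stopping at the fifth early death among the first 10 patients is the same event and keeps the same closing probability at every true rate.

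A reader might infer that the stated 15% or 8% is wrong, or that error rates would improve. Neither follows: both figures reproduce, and curtailment changes only when accrual ends. The equality applies to deaths among the first 10 patients of the arm; counting deaths beyond the tenth would be a different rule.

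The benefit, about 0.5 to 2.2 patients per closing arm across rates of 27-60%, rests on the assumed accrual of one patient per arm every 1 to 3 weeks and uniform death times.

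**What to change.** In section 14.4, for the early-death rule only and in both arms, write:

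> Accrual to the arm stops as soon as the fifth early death (on or before day 28) occurs among its first 10 patients; otherwise early death is evaluated after 10 patients as planned.

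Leave the timing and wording of the inefficacy look unchanged. Add one sentence stating that the between-arm comparison is not made once an arm has closed. In reporting, note that a curtailed arm has fewer than 10 patients and that its observed early-death proportion reflects the stopping rule.

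The cost is one sentence per arm and a running tally of deaths at a single center. The 5-of-10 boundary, the maximum sample size and all stated probabilities stay as they are. The price is less precise estimates in a curtailed arm and no between-arm comparison involving it.

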Since 2012, we have used G-CLAM extensively in adults with newly diagnosed AML and high-grade MDS, primarily as part of a large, ongoing institutional phase 1/2 trial (FHCRC #2734.00). Our interest in this regimen stems from data indicating improved anti-leukemic activity with regimens containing cladribine, high-dose cytarabine, and escalated doses of mitoxantrone compared to standard 7+3 chemotherapy. Data from this trial, which was presented at the 2016 annual meeting of the American Society of Hematology, have established the safety of a G-CLAM regimen with escalated doses of mitoxantrone, which will form the basis for the backbone used in this proposal. Specifically, the phase 1 portion on 33 patients established the highest dose tested (mitoxantrone at 18 mg/m²/day) as the maximally tolerated dose. A total of 62 patients, including 6 treated in phase 1, received G-CLAM at MTD. Patient characteristics were as follows: median age 58 (21-81) years, median TRM score 2.85 (0.06-6.73), with AML (n=52) or high-risk MDS (n=10). Cytogenetics were favorable in 6, intermediate in 44, and adverse in 12 (MRC criteria); 11 patients had NPM1 and 6 had FLT3 mutations. Fifty-two patients (83.9%, 95% confidence interval: 72.3-92.0%) achieved a CR (n=48 [77.4%: 65.0-87.1%]), or CRp/i (n=4 [6.5%: 1.8-15.7%]) with 1-2 cycles of therapy. Only 3 patients required 2 cycles to best response. Among the 48 CR patients, 43 (89.6%) were negative for measurable residual disease (MRD^{neg}) by flow cytometry. Four patients had morphologic leukemia free state, 1 patient with myeloid sarcoma had a partial remission, 4 had resistant disease, and 1 died from indeterminate cause. One patient died within 28 days of treatment initiation (septic shock). Median times to an absolute neutrophil count \geq 500/ μ L and a platelet count of \geq 50,000/ μ L were 26 and 23 days. Besides infections and neutropenic fever, maculopapular rash, and hypoxia (fluid overload/infection-related) were the most common grade \geq 3 adverse events. In addition to the phase 1/2 MTD cohort, there were 15 patients treated in an expansion cohort and 3 eligible patients treated off protocol with mitoxantrone at 18 mg/m². For these 80 patients combined treated at MTD, the CR and CR/CRp/i rates were 76.3% and 81.2%. After multivariable adjustment, compared to 300 patients treated with 7+3 on the SWOG S0106 trial, G-CLAM with mitoxantrone 18mg/ m² was associated with an increased probability of CR (odds ratio [OR]= 3.08, p=.02), CR/CRp/i (OR=2.96, p=.03), a trend towards improved MRD^{neg} CR (OR= 3.70, p=.06), and a trend towards improved overall survival ([OS]; hazard ratio=0.34, p=.07). For the entire study cohort, the 6 and 12-month relapse-free survival were 73% (64-83%) and 62% (42-74%) and the 6 and 12-month OS were 89% (82- 96%) and 77% (67-88%). Together, our study found G-CLAM with mitoxantrone up to 18 mg/m²/day to be well tolerated and to have potent anti-leukemia activity.

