3.0 PATIENT ELIGIBILITY

3.1 Inclusion Criteria

- 3.1.1 Age ≥ 18 years
- 3.1.2 Diagnosis of untreated “high-grade” myeloid neoplasm ($\geq 10\%$ myeloid blasts by morphology in bone marrow and/or peripheral blood) or AML other than acute promyelocytic leukemia (APL) with t(15;17)(q22;q12) or variants according to the 2016 WHO classification.¹⁶ Patients with acute leukemias of ambiguous lineage are eligible. Outside diagnostic material is acceptable as long as peripheral blood and/or bone marrow slides are reviewed at the study institution and cytogenetic/molecular information is available.

- 3.1.3** Treatment-related mortality (TRM) score ≥ 13.1 as calculated with simplified model (see APPENDIX A).¹²
- 3.1.4** The use of hydroxyurea before enrollment is permitted; hydroxyurea should be discontinued prior to start of study treatment. Patients with symptoms/signs of leukostasis, WBC $>100,000/\mu\text{L}$, or acute symptoms felt related to their high-grade myeloid neoplasm can be treated with leukapheresis or may receive up to 1 dose of cytarabine (up to 500 mg/m²) anytime prior to study day 1.
- 3.1.5** Patients may have received treatment (e.g. azacitidine/decitabine, lenalidomide, growth factors) for antecedent low-grade myeloid neoplasm.
- 3.1.6** Left ventricular ejection fraction (LVEF) $\geq 45\%$, assessed within 3 months prior to registration, e.g. by MUGA scan or echocardiography, or other appropriate diagnostic modality.
- 3.1.7** Women of childbearing potential and men must agree to use adequate contraception beginning at the signing of the consent until at least 4 weeks after the last dose of study drug.
- 3.1.8** Ability to understand and the willingness to sign a written informed consent document

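### Section 14.4 gives each arm one absolute early-death rule, at 10 patients, and no early-death boundary for the second stage

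*Combined protocol and SAP*

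**What the plan says.** Section 14.4 sets out the first stage: "In the first stage, 10 patients will be accrued to each arm, either in a randomized or non-randomized fashion". The endpoint is fixed: "Early mortality will be defined as death for any reason on or before day 28 after starting therapy". For the lower-dose arm, "After 10 patients have been accrued to the lower-dose arm, we will evaluate for early death and inefficacy", and "If the number of early deaths is 5 or higher, accrual will stop". The higher-dose arm has identical wording. The only operating characteristic given for this rule is a 15% chance of stopping at a true rate of 30%. The stated control is the institution's CPX-351 trial, with 10 early deaths in 37 patients (27%).

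The same section adds two other ways for an arm to close:
- an inefficacy rule (no MRD-negative CR in the first 10 patients);
- a between-arm Fisher test of early mortality, and another of MRD-negative CR, at the 10% level once each arm has at least 10 patients. The faster arm may have more than 10 by then.

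Accrual then continues to 50 in total. Arm sizes are not fixed, because patients who decline randomization choose their arm (section 14.1). Section 14.3.1 says that if one arm closes early, "the remaining patients will be treated on the remaining arm".

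**The concern.** The section is introduced as a two-stage design that allows early stopping, yet the second stage has no early-death boundary. An arm that passes with 4 deaths in its first 10 patients meets one relative comparison with the other arm and then no further numeric trigger.

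Most of an arm's patients may enter after its only absolute look: 15 of 25 in a balanced trial, or about 30 of 40 if the other arm stops at 10. In that last case there may be no open comparator either.

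The plan also gives no probability of stopping an arm whose early mortality is too high. A committee reading it cannot tell how much protection a pass at 10 patients gives.

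**Working it through.** **Inputs.** From section 14.4: 10 patients per arm at the look, stop at 5 or more early deaths, control rate 27%, Fisher test at 10%, maximum 50 patients. True rates of 40% and 50% are assumptions made here to show the range; they are not in the documents.

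**1. The plan's own figures.** With X binomial (10, p), P(stop) = 1 − P(X ≤ 4). At p = 0.30: 1 − (0.0282 + 0.1211 + 0.2335 + 0.2668 + 0.2001) = 0.150, matching the stated 15%. The inefficacy figure also reproduces: 0.78^10 = 0.083 (8% stated). The two Fisher examples give two-sided p = 0.087 (0 v 4 of 10) and 0.070 (2 v 7 of 10), both below 0.10 as stated.

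**2. The same rule at other rates.** At p = 0.50, P(pass) = (1 + 10 + 45 + 120 + 210)/1024 = 386/1024 = 0.377.

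| True early-death rate | P(stop at 10) | P(pass) |
|---|---|---|
| 27% | 10% | 90% |
| 30% | 15% | 85% |
| 40% | 37% | 63% |
| 50% | 62% | 38% |

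**3. Adding the between-arm test, 10 v 10.** Among results that pass the within-arm rule, only 4 v 0 is significant (p = 0.087); 3 v 0 gives 0.21 and 4 v 1 gives 0.30. For an arm at 50% and another arm at rate q, P(pass both) = 0.377 − P(X = 4) × (1 − q)^10, with P(X = 4) = 210/1024 = 0.205.

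| q (other arm) | (1 − q)^10 | P(pass both) |
|---|---|---|
| 50% | 0.001 | 38% |
| 30% | 0.028 | 37% |
| 27% | 0.043 | 37% |
| 20% | 0.107 | 35% |
| 10% | 0.349 | 31% |
| 5% | 0.599 | 25% |

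If the 50% arm accrues faster and has 15 to 25 patients at the comparison, exact enumeration gives 33-35% with the other arm at 27-30%, and 11-22% with it at 5-10%.

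**4. Adding the inefficacy rule instead.** Assume that early deaths are not responders, and let r be the MRD-negative CR rate among all patients in the arm. Then P(pass both within-arm rules) is the sum over d = 0 to 4 of P(X = d) × [1 − (1 − r/0.5)^(10 − d)]. This gives 37% at r = 22%, 29% at 10% and 19% at 5%.

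**5. Exposure after the look.** Balanced: 50/2 = 25 per arm, so 15 patients after the look. If the other arm stops at 10: 50 − 10 = 40, so 30 after the look.

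**6. Effect of repeating the absolute check.** The calculation carries forward the death counts that have not yet stopped. At 50%, the look at 20 (10 or more deaths) adds 0.205 × 0.377 + 0.117 × 0.172 + 0.044 × 0.055 + smaller terms = 0.100, so P(stop) = 0.623 + 0.100 = 0.723.

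| Looks (cumulative) | 30% | 40% | 50% |
|---|---|---|---|
| 5 of 10 (current) | 15% | 37% | 62% |
| plus 10 of 20 | 16% | 42% | 72% |
| plus 14 of 30 | 17% | 48% | 82% |

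The last row applies only to an arm that reaches 30 patients.

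**The case against.** The strongest answer is that early mortality is examined more than once. The between-arm test can close an arm, sometimes on more than 10 patients. The inefficacy rule catches a regimen under which few patients respond. Section 9.0 provides independent DMC review of toxicity. Section 12.0 provides committee review at least annually and as needed, covering adverse events and stopping rules. Section 17.0 lets the principal investigator or IRB terminate at any time. All of this stands, so a reader who infers that an arm is looked at once and never checked again goes further than the documents allow. What remains is that none of these supplies an absolute early-death boundary after patient 10. The Fisher test is described once, is relative, and cannot detect high mortality shared by both arms.

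Two other readings are tempting and also fail:
- The earlier G-CLAM cohort had TRM scores up to 6.73, against the 13.1 or more required here, so one might infer that the rule has no relevant reference. Section 14.4 does not use that cohort. Its control is the CPX-351 trial, which it describes as having essentially the same eligibility criteria.
- Because "Accrual may temporarily be held while outcome data on these patients matures", one might infer that accrual can continue into an arm known to have met its boundary. The text says accrual will stop at 5 deaths. The optional hold only governs entry while day-28 status is pending, and it does not produce the 38%.

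The benefit of more looks is also modest in a balanced arm. Counting the within-arm rule alone, with no overrun, expected early deaths after patient 10 at a 50% rate are 0.377 × 15 × 0.5 = 2.8 now. With a look at 20 they are 0.377 × 10 × 0.5 + 0.277 × 5 × 0.5 = 2.6. In a 40-patient arm they fall from 0.377 × 30 × 0.5 = 5.7 to 0.377 × 5 + 0.277 × 5 + 0.184 × 5 = 4.2 with looks at 20 and 30. The gain lies mainly in the large-arm case, which the plan allows.

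**Conclusion.** The point holds as a gap in the monitoring plan that is cheap to close; it is not an error in the plan's arithmetic, which reproduces. Each arm has one absolute early-death rule and one relative test, and the second stage has no early-death boundary.

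An arm with a true early-death rate of 50% passes the within-arm rule 38% of the time, and one at 40% passes 63% of the time. Both are upper bounds on passing the whole plan. With 10 v 10 patients, the between-arm test leaves the 38% near 37% if the other arm is at 27-30% and lowers it to 25-31% if the other arm is at 5-10%. The inefficacy rule can lower it further.

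These figures rest on the assumed 40% and 50% rates and on independent outcomes. The arm size of 40 assumes that the other arm stops at 10.

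**What to change.** In section 14.4, keep the look at 10 and add absolute within-arm early-death checks through the rest of accrual. State that they continue after the other arm has closed and run to the largest size an arm can reach. Give the operating characteristics at 30%, 40% and 50%.

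The boundaries of 10 of 20 and 14 of 30 are illustrations only. A further look is needed to cover patients 31 to 40, and the sponsor should choose the exact boundaries.

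The cost is a few lines of text and no new data, since day-28 status is already needed for the existing rule. The false-stop chance at a 30% rate rises from 15% to about 16-17%, and slightly more with a further look. Whether to make the accrual hold mandatory is a separate trade-off between accrual time and patients entered while outcomes are pending. It is for the sponsor to decide and is not part of this recommendation.
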